### Decision-making tree for Moovcare web -application alerts

In the event of a relapse or complication, the treatments will be left to the discretion of the investigators. The application will be used during the treatment of the relapse or complication at the same rate.

CONFIDENTIAL

## **5.5. IDENTIFICATION OF ALL SOURCE DATA NOT APPEARING IN THE RECORDS**

The satisfaction and quality of life questionnaires will not be in the patient's source record. They will be made available in a pocket per patient in the investigator file so that they can be transcribed in the e-CRFs. On the other hand, the self-assessments carried out by the patients will not be in the source file, they will be carried out directly on the Moovcare web application.

The other data relating to the patient and necessary for his follow-up outside the trial, will be collected in his medical file.

## **5.6. RULES FOR SUBJECT WITHDRAWAL**

### **5.6.1. Criteria for a study subject's early withdrawal**

Patients can withdraw their consent and request to withdraw from the trial at any time and for any reason, without losing the right to be treated by their doctor. The investigator may also prematurely discontinue a patient's participation in the trial for any reason that would serve the best interests of the patient, including the case of an intercurrent disease or an adverse event. In the event of premature discharge, at any time and for any reason, the investigator should notify the patient, if necessary, and document the reasons as fully as possible.

Test exits must be reported in particular for the following possible reasons:

- Death,
- Withdrawal of consent with the patient's request not to use the data already collected,
- Wrongly included,
- Choice of investigator,
- Patient choice,
- No seizure in the application for 6 consecutive weeks apart from a pathology or relapse preventing seizure,
- Lost view.

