### **2.2.2. Secondary endpoints**

Progression-free survival is defined as the time between the date of the first examination making the diagnosis of partial response or complete response and the date of consultation allowing the diagnosis of the relapse.

The diagnosis of partial or complete response, as well as relapse in this study follows the definition of the Cheson criteria.

The time between the date of diagnosis of the relapse and the nearest consultation date scheduled as part of the standard follow-up will be evaluated. The same will be done with the date of diagnosis of significant complications.

The time taken to set up a treatment will also be evaluated. Thus, the time between the date of diagnosis of each event and the date of implementation of the care (1st psychological consultation, date of D1 of treatment, etc.) will be evaluated.

Overall survival is defined as the time between the date of diagnosis of the complete or partial response as defined in chapter 2.1.2 and death from any cause within 2 years.

Quality of life will be studied using the QLQ-C30 and HUMEUR PhQ9 questionnaires at inclusion and then follow-up consultations at 3, 6, 9 and 12 months.

Patient compliance with the use of the web application will be assessed based on the number of assessments completed by patients; an evaluation every 14 days is expected. Patients who have completed less than 1 assessment per 42 days (6 weeks) will be considered non-compliant. An overall compliance rate over the entire period and a rate per 14-day period can then be presented.

The satisfaction and feelings of patients with regard to the web-monitoring and the use of the web-application will be assessed by a self-questionnaire during the follow-up visit in the 6th month.

The calculation of the application's sensitivity is based on the evaluation of the number of alerts triggered by the application against the results of systematic or alert-triggered imaging examinations.

CONFIDENTIAL

The Performance Status will be assessed according to WHO recommendations.

The description of health consumption will be assessed by the number of consultations, imaging and laboratory tests performed by the patients in each group.

[figure not shown]

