## **5.2. *STUDY EVALUATIONS***

The type of follow-up the patient will benefit from will be assigned by randomization.

Patients will be able to benefit from the supportive care adapted to their situations. The need for this supportive care can be detected during consultations or through the application.

All patients will be seen in consultation every 3 months with a clinical examination including estimation of the PS and a biological assessment (according to the clinician's habits).

The questionnaires (QLQ-C30 and PhQ-9) will be completed again at the 3,6-,9- and 12-month follow-ups.

For patients randomized to the "standard" arm, a systematic imaging workup (minimum TAP CT (cervical at best)) will be performed every 6 months corresponding to standard follow-up.

Patients randomized to the "Web-application follow-up" arm will perform a self-assessment of symptoms via the Moovcare application with a maximum interval of 14 days between 2 seizures, and if necessary, each time symptoms appear.

In the event of a Moovcare alert (and telephone call to the patient) suggesting a relapse or a complication, a CT scan and / or other evaluation examination (PET, biopsies, etc.) will be scheduled within ideally less than 14 days depending on the type of alert.

CONFIDENTIAL

To be able to connect to the application, included patients will receive personal access codes to the application by email with instructions for use:

- access to the application is via a username and password,
- the password is encrypted in the host's database,
- access to the application is via a secure SSL connection (https) which is a protocol for securing data exchanges between the client and the application server,
- a brute force intrusion detection system makes it possible, when too many connection attempts are detected, to deactivate the account in question.

A satisfaction questionnaire will be taken at the 6-month follow-up.

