### **5.6.2. Procedure for a study subject's early withdrawal**

The terms of medical care and follow-up in the event of premature discontinuation of the study for a given patient will be identical to those usual outside the protocol.

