### **5.6.3. Study termination criteria (excluding biostatistics considerations)**

The end of the research will be defined as the last follow-up visit (at 24 months) of the last patient included.

In addition, the study may be interrupted for administrative reasons, and / or by decision of the promoter. If the study is terminated prematurely or suspended, the study leader will immediately inform the Ethics Committee of the reason for the termination or suspension. In all cases, the patients included will be followed as part of the study until the 24-month follow-up visit by the investigator.

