## **6.2. STATISTICS**

### **6.2.1. Description of planned statistical methods**

This study should allow us to evaluate the functioning of the application in a follow-up context in patients with lymphoma at high risk of relapse.

The patient sample for this analysis will consist of all patients, included in the study and meeting all the eligibility criteria described in Chapter 4, who have signed a consent.

The initial characteristics of the analysis population (demographic data, disease, previous and concomitant treatments, prognostic factors, etc.) and all the evaluation criteria described in paragraph 2 will be presented globally

For the qualitative variables, we will present the number as well as the percentage. For quantitative variables, we will present the median or the mean plus or minus the standard deviation depending on the normality of the variable, the minimums and maximums will also be indicated.

Events, as defined in chapter 2.1.2. (apart from relapse) will be described in terms of frequency by etiological type (HLT or HLG T according to the MedDRA classification) and by severity according to NCI CTCAE v4.02.

For the analysis of the censored data (overall survival and other timeframes of events), the survival curves will be plotted according to the Kaplan-Meier estimates, the medians of survival will be presented as well as their 95% confidence intervals.

For performing multivariate survival analyzes, the semi-parametric Cox model will be used to calculate the odds ratios which will be presented with their 95% confidence interval.

The sensitivity of the application to detect a relapse and / or significant complications will be calculated.

Quality of life scores will be calculated according to EORTC guidelines for the QLQ-C30. The quality of life will be described at each measurement time and compared to inclusion and then studied longitudinally using mixed analysis of variance models for repeated measures.

PHQ9 scores will be calculated according to the recommendations, described at each measurement time and compared to inclusion. The classes proposed in the literature ( $\leq 4$ ; 5-14;  $> 14$ ) will be used to describe the state of depression of patients.

The analyzes will be carried out with SAS 9.3 software (SAS Institute Inc. Cary, NC, USA).

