### **6.2.1. Sample size determination**

The main objective of the study is to show that follow-up via the SENTINEL Lymphoma web-application could make it possible to better identify the significant complications occurring between two systematic follow-up consultations with the specialist in patients followed for high-risk lymphoma. relapse than with standard follow-up. The evaluation of the main objective will be carried out over 6 months of follow-up.

This study is based on a pooled triangle test analysis (24, 25, 26). Two groups will be composed, one will be monitored via the web-application, the other will be monitored in a standard way (consultation and imaging).

A 1: 1 randomization will assign the treatment group to the patient. Stratification on center, autologous transplant, PS, relapse and lymphoma type will be performed to ensure the comparability of our two populations at inclusion.

This sequential method will make it possible to evaluate during recruitment the diagnostic efficiency of significant complications outside systematic consultations while controlling the power (risk of accepting our null hypothesis wrongly) and the type I error (risk of rejecting our wrongly null hypothesis). This design allows us to consider stopping the trial as soon as the information gathered is sufficient to conclude. We will be able to conclude that the web-application is diagnostic efficiently or, on the contrary, that it is lacking in interest.

We set the risk of the first species alpha at 5%, the potency at 90%, we envisage that monitoring via the web-application allows us to identify significant complications between two systematic follow-ups in 90% of patients (i.e. 10% of patient presenting an event not identified early) against 60% (i.e. 40% of patient presenting an event not identified early) in the group followed in a standard way (i.e. a difference of 30%).

The early unidentified event is defined:

- in the web application follow up group by the absence of an alert in the following cases:
  - emergency hospitalization,
  - a medical consultation without follow-up with medical prescription (imaging / drug prescription)
  - a significant event at the classic follow-up consultation (very degraded PS, antibiotic therapy, supportive care with consultation, pulmonary embolism, sepsis, severe depression, etc.)
  
- – in the standard group in the following cases:

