## ***7.3. MODALITIES AND DURATION OF THE FOLLOW-UP OF PERSONS FOLLOWING THE OCCURRENCE OF ADVERSE EVENTS***

All the patients included in the study are followed for 2 years (24 months).

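### Six weeks without an app entry is a trial exit that only web-arm patients can meet, and the plan does not settle whether their 6-month primary outcome is still collected

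*Combined protocol and SAP*

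**What the plan says.** - **Exit reason.** Section 5.6.1 lists the trial exits to be reported. One is "No seizure in the application for 6 consecutive weeks apart from a pathology or relapse preventing seizure". Sections 5.2 and 5.3 assign app self-assessment to the web arm only, so no standard-arm patient can meet it. The other listed reasons (death, withdrawal of consent, wrong inclusion, investigator or patient choice, loss to follow-up) can arise in either arm.
- **After an individual exit.** Section 5.6.2 says that care and follow-up "will be identical to those usual outside the protocol". It does not mention trial data.
- **Text pointing the other way.** Section 5.6.3, after its sentences on stopping the whole study, says "In all cases, the patients included will be followed as part of the study until the 24-month follow-up visit by the investigator". Section 7.3, on follow-up after adverse events, also states that included patients are followed for 24 months.
- **Compliance.** Section 2.2.2 describes a similar gap without calling it an exit: "Patients who have completed less than 1 assessment per 42 days (6 weeks) will be considered non-compliant".
- **Analysis sample.** Section 6.2.1 (planned methods): "The patient sample for this analysis will consist of all patients, included in the study", provided they are eligible and consented. It gives no rule for a missing 6-month outcome.
- **Failure definition.** Section 6.2.1 (sample size) defines an event not identified early "in the web application follow up group by the absence of an alert in the following cases": emergency hospitalisation, an unscheduled consultation with a prescription, or a significant event at the routine visit. The standard-arm list has no item for unscheduled consultations.

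**The concern.** A patient who makes no entries cannot generate a symptom alert. Under the web-arm definition, any listed complication in such a patient is a failure. These are the patients whom section 5.6.1 allows to leave the trial, and the standard arm has no matching exit.

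If the outcome is not collected after this exit, web-arm information is lost for a reason tied to use of the intervention, and the two arms are no longer comparable as randomised. The trial is open-label with at most 40 patients per group, so a shift of one or two failures changes the error rate noticeably. The plan does not say whether an exited patient without later data would be scored event-free, scored as a failure or left out.

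**Working it through.** **Inputs from section 6.2.1 (sample size).** At most 40 per group; failure 40% in the standard arm and 10% in the web arm; alpha 5%; power 90%; two analyses; 6-month outcome.

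**Assumptions, because the documents are silent.** Web-arm exit share w = 5%, 10% or 20% (2, 4 or 8 of 40 patients), the exits' failure risk, and how they are scored. The test is a single-look pooled z-test, with success for the app declared at z ≥ 1.96, evaluated by exact binomial enumeration.

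**Step 1: the plan's own size.** The fixed-design two-sided formula for 60% against 90% with 90% power gives 41.7, so 42 per group. A two-look triangular test on the log odds ratio at one-sided 2.5% gives 38.9. The stated 40 reproduces, with no allowance for exits.

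**Step 2: no true effect, complete data.** Failure is 40% in both arms. The chance of a false result for the app is 2.6%.

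**Step 3: no true effect, exits at average risk, scored event-free after exit.** If a fraction f of their failures is recorded before exit, the observed web failure rate is 0.40 × [1 − w(1 − f)].

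| | w = 5% | w = 10% | w = 20% |
|---|---|---|---|
| Half recorded (f = 1/2): observed rate | 0.390 | 0.380 | 0.360 |
| False-positive chance | 3.2% | 3.9% | 5.6% |
| All exit at week 6 of about 26, constant event rate (f = 6/26): observed rate | 0.385 | 0.369 | 0.338 |
| False-positive chance | 3.6% | 4.8% | 8.2% |

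Week 6 is the earliest possible exit, so the second scenario is the maximum under a constant event rate. In failures, at w = 20% the exits account for 8 × 0.40 = 3.2 of the 16 expected in the web arm. With half recorded, 1.6 are lost; with exit at week 6, 3.2 × 20/26 ≈ 2.5.

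**Step 4: no true effect, exits dropped.** This leaves 38, 36 or 32 web patients. If the exits' risk is r, the remaining patients' risk is (0.40 − w·r)/(1 − w).

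| Exits' risk r | Remaining patients' risk | w = 5% | w = 10% | w = 20% |
|---|---|---|---|---|
| 40% | 0.400 / 0.400 / 0.400 | 2.5% | 2.5% | 2.3% |
| 60% | 0.389 / 0.378 / 0.350 | 3.1% | 3.9% | 5.9% |
| 20% | 0.411 / 0.422 / 0.450 | 2.0% | 1.6% | 0.8% |

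The direction therefore depends on who exits and how they are scored.

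**Step 5: does the sequential design change the picture?** The triangular boundaries are not stated. With assumed boundaries (one-sided 5%, looks at 20 and 40 per group), the false-positive chance is about 4.8% with complete data. With event-free scoring and half the exits' failures recorded it is 5.6/6.5/8.6%. The pattern is the same.

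**Step 6: power if exits are followed and analysed as randomised.** Suppose non-users fail at 40% and users at 10%. The web rate is 0.10(1 − w) + 0.40w, which is 0.13 at w = 10% and 0.16 at w = 20%. The difference falls from 30 points to 27 or 24. Single-look power at 40 per group falls from 90% to about 80% or 68%.

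**The case against.** The strongest reply is that no sentence says data collection stops. Section 5.6.1 is a list of exits to report, and its reasons are called possible, so removal may not be automatic. The list includes death, whose date is itself a survival outcome. It singles out consent withdrawal with refusal of data use, which suggests that data from other exits are kept. Section 5.6.2 speaks of medical care and follow-up, not of the case report form. Sections 5.6.3 and 7.3 promise 24 months. Read literally, section 6.2.1 keeps the exited patient in the analysis and would count a complication without an alert as a failure. The compliance threshold in section 2.2.2 can also coexist with an exit reason.

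Most of this stands, and it limits what can be concluded. A reader might infer that the plan discards web-arm failures and so biases the trial towards the app. The documents do not support that: loss of data is not stated, event-free scoring appears nowhere, and dropping low-risk exits works against the app. A reader might also treat every failure among the exits as lost, which would give 3.9/5.6/11%. Under a constant event rate that cannot happen, because exit requires a six-week gap and a complication in that gap already precedes the exit. The exception for illness or relapse also makes high-risk exits less likely.

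What the reply does not do is supply a rule. The only text on individual exit points to follow-up outside the protocol, the two 24-month sentences sit in other contexts, and the exit reason still exists in one arm only.

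**Conclusion.** The point holds as a one-arm exit rule combined with conflicting text on follow-up after exit. It should be fixed before the primary comparison is relied on. If outcomes are lost after this exit, comparability of the arms is damaged by an amount and in a direction that the documents do not allow anyone to determine.

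Under the assumed 5 to 20% exits, the single-look false-positive chance for the app, 2.6% with complete data, lies between 0.8% and 8.2% across the scenarios shown. The upper end needs event-free scoring and every exit at week 6. If average-risk exits are dropped, the effect is about neutral. The stated sample size is not in error. Confidence is medium, because everything about size rests on an exit rate and a scoring rule that the plan does not give.

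**What to change.** 1. Reconcile sections 5.6.1, 5.6.2, 5.6.3 and 7.3 so that they say one thing about follow-up after an individual exit.
2. State that after any exit, including app non-use, the 6-month primary outcome, relapse and survival are still collected unless the patient withdraws consent. The visits already exist: "All patients will be seen in consultation every 3 months with a clinical examination" (section 5.2).
3. In section 6.2.1, analyse all randomised patients in their assigned arm under the existing failure definitions, with one pre-specified rule for missing outcomes, whatever the exit reason, applied to both arms.

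What surveillance a non-user receives is for the sponsor to decide; this point concerns outcome collection only.

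**Cost.** Text changes, and data entry at scheduled visits. The as-randomised effect may be smaller than planned. If 10% or 20% stop using the app and fail at 40%, single-look power is about 80% or 68%. To restore 90% would take about 55 or 72 per group, against 42 by the same formula at planning values. Power would be lower still if non-users fail more often than 40%. That is possible, because the web-arm failure list also counts unscheduled consultations with a prescription.

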### **5.6.2. Procedure for a study subject's early withdrawal**

The terms of medical care and follow-up in the event of premature discontinuation of the study for a given patient will be identical to those usual outside the protocol.

### **5.6.3. Study termination criteria (excluding biostatistics considerations)**

The end of the research will be defined as the last follow-up visit (at 24 months) of the last patient included.

In addition, the study may be interrupted for administrative reasons, and / or by decision of the promoter. If the study is terminated prematurely or suspended, the study leader will immediately inform the Ethics Committee of the reason for the termination or suspension. In all cases, the patients included will be followed as part of the study until the 24-month follow-up visit by the investigator.

## **6. DATA MANAGEMENT ET STATISTICS**

### ***6.1. STUDY DATA COLLECTION AND PROCESSING***

#### **6.1.1. Data collection**

An electronic observation log (e-CRF) (ENNOV Clinical®, Cenon, France) will be created per patient. All the information required by the protocol will be collected in the e-CRF. It will include the data necessary to confirm compliance with the protocol and detect major deviations from the protocol, as well as all the data necessary for statistical analyzes.

The person (s) responsible for filling in the e-CRFs (investigator, CRA, etc.) must be defined and identified in the table of delegations of responsibilities for each center (kept in the investigative workbook).

#### **6.1.2. Data coding**

By signing this protocol, the principal investigator and all investigators agree to keep confidential the identities of the patients who participated in the study.

The information required by the protocol will be collected without mentioning the first and last name in the e-CRF with an identification number for the center and a patient number. Only the first letters of the patient's first and last name will appear.

This code will be the only information that will appear in the observation notebook (e-CRF) and which will allow the e-CRF to be linked to the patient posteriori.

The sponsor is also required to encode the patient data on all documents he may have in his possession (reports of imaging examinations, biology, etc.) which would be attached to the e-CRF.

#### **6.1.3. Data processing**

For each patient, all the data will be collected in the e-CRF. The latter will be completed by the investigator and / or the CRA designated for this task.

The processing of the trial data is carried out by the sponsor; the data being the property of Weprom, promoter of the research.

The data processing software are ENNOV Clinical® (Cenon, France) and SAS 9.3 (SAS Institute Inc. Cary, NC, USA) software.

In accordance with the revision of the Data Protection Act of August 6, 2004 and its implementing decree, Weprom has undertaken to follow the MR001 reference methodology of the National Commission for Computing and Liberties.

